9.5 STOPPING RULES

In addition to the safety and feasibility criteria used in the primary endpoint (Section 9.1), we will also monitor a specified set of treatment related serious adverse events (TRSAEs) within the defined treatment period. This is the period of up to 8 weeks (or the allowed grace period in special circumstances defined in section 9.6) from initiation of oral therapy until evaluation at the clinical center. This safety monitoring is to ensure that the rate of TRSAEs does not substantially exceed an anticipated rate. The following TRSAEs will be monitored for early stopping of the study:

- Death considered to be probably or definitely related to the oral treatment during the study treatment period
- Any grade IV toxicities considered to be probably or definitely related to the treatment
- Death related to misdiagnosis and delay in appropriate treatment

The study will be monitored using the stopping rules as outlined below for early stopping if the number of subjects in the study who have developed one or more of the above specified TRSAEs is over a pre-specified threshold value. TRSAEs are those attributed as definitely or probably related to eltrombopag.

From our experience using this agent in other clinical settings, we anticipate the rate of developing at least one of the above specified TRSAEs for this patient population to be 20% or less. Our stopping rule is determined by a Bayesian approach based on Geller et al. publication[44]. The stopping boundary for the study is reached if the Bayesian posterior probability that the true probability of developing one or more of the above specified TRSAEs exceeds this benchmark rate of 20% is at least 90%. We take our prior distribution to be a beta distribution with the sum of the two beta parameters to be 5.5, i.e. the parameters of the beta prior distribution are 1.10 and 4.40. Since we have seen in the past that the first few subjects to be accrued are possibly sicker than the rest of the subjects in the sample, we will start safety monitoring the study when 3 or more subjects have developed specified TRSAEs. The following tables summarize the threshold numbers for stopping the study:

Number of Tx subjects enrolled	Stop if the number of Tx subjects who develop any of the specified TRSAEs reaches:
≤ 5	3
≤ 8	4
≤ 12	5
≤ 16	6
≤ 20	7
≤ 24	8

Abbreviated Title: Early Initiation of Oral Therapy for Naïve Severe Aplastic Anemia (SAA)

Version Date: 11/05/2025

Number of Tx subjects enrolled	Stop if the number of Tx subjects who develop any of the specified TRSAEs reaches:
≤ 28	9
≤ 32	10
≤ 36	11
≤ 39	12

For a simulation study of the stopping rule, we generated a study with 39 independent Bernoulli trials, each had a probability p for having the above TRSAE and $q=1-p$ for not having such TRSAE and compared the TRSAE outcomes with the above stopping boundary to determine whether the study was stopped. We repeated the simulation 100,000 times and computed the proportion of stopped studies (i.e. “number of stopped studies”/100,000), which were stopped using the above stopping rule. The following table summarizes the proportions of stopped studies under a number of scenarios for p :

Probability of Monitored” TRSAE= p	5%	10%	15%	20%	25%	40%
Proportion of stopped studies	0.15%	1.62%	7.26%	21.74%	44.48%	95.30%
Average number of Tx subjects	38.95	38.51	37.08	33.80	28.80	13.32
Average number of Tx with a specified TRSAE	1.95	3.85	5.56	6.76	7.20	5.33

The above results suggest that the above stopping rules have a low probability of stopping a study when the proportion of the corresponding specified TRSAE is below the benchmark value of 20%, and the probability of stopping a study is high when the true proportion of the above specified TRSAE exceeds this benchmark value. Based on these results, we believe that our Bayesian stopping rules have satisfactory statistical properties.

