3 STUDY DESIGN

This study is designed as a non-randomized, pilot study in which subjects with SAA will be started with investigational early initiation of CsA and EPAG either before arrival to the NIH or at the NIH while work up is being completed. When the treatment is initiated remotely, it will be under oversight of investigators at NHLBI. At the CC, patients will receive standard treatment with higher dose CsA, EPAG, and h-ATG. h-ATG may be omitted if complete response is achieved.

Cohort 1 (original, n=39)

*D1 – Patients will be evaluated and enrolled at the NIH if able to arrive for initial visit within 72 hours of referral. If ANC <200 at the initial visit at NIH, treatment with all three drugs may be initiated without waiting for the cytogenetics.

**h-ATG may be omitted in patients who have achieved a complete response at the initial NIH visit after initiating oral treatment remotely

Note: Study treatment period of 8 weeks may be extended as defined in Section 9.6

Extension Cohort (n=41, same study design as above)

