5 TREATMENT PLAN

Patients will commence therapy with cyclosporine and eltrombopag as outpatients (if transfer to the Clinical Center is anticipated to require >72 hours or upon evaluation to the Clinical Center if <72 hours). Medications will be shipped to the patient at their provided address. After beginning cyclosporine and eltrombopag, monitoring blood work will be obtained at least weekly, more frequent if clinically indicated. For outpatients, a member of the NIH bone marrow failure team (research nurse, physician assistant, or physician) will speak by telephone with the patient or responsible family member every week, to ascertain symptoms and for any evidence of drug toxicity or intolerance (Appendix B). Within 8 weeks after consent, all subjects will have their evaluation at the Clinical Center except if grace period is granted in special circumstances (defined in Section 9.6) and receive the standard treatment with h-ATG, higher dose cyclosporine (3mg/kg twice a day), and eltrombopag daily after full work up is completed here. For patients without grace period extension, the evaluation will take place within 8 weeks of initiation of oral treatment but the administration of the standard treatment may not occur within the 8 weeks' time frame. If ANC <200 at the initial visit at NIH, treatment with all three drugs may be initiated without waiting for the cytogenetics.

If participants are unable to come to the NIH due to unanticipated reason beyond their control, the administration of the standard treatment with h-ATG, higher dose cyclosporine, and continuation of eltrombopag daily may be performed by subject's local physician/institution with guidance from the NIH bone marrow failure team after the full work up is completed as listed in section 6.1 (Clinical studies to be performed at the Clinical Center on first visit) and results reviewed by the NIH bone marrow failure team. If this is to occur, specialized studies (marked as * in section 6.1) may be omitted.

Abbreviated Title: Early Initiation of Oral Therapy for Naïve Severe Aplastic Anemia (SAA)

Version Date: 11/05/2025

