9 BIOSTATISTICAL CONSIDERATIONS

9.1 PRIMARY ENDPOINTS

The primary endpoint of this pilot study is to evaluate the safety and feasibility of rapid initiation of oral treatment regimen, CsA + EPAG prior to receiving standard regimen at the Clinical Center in treatment naïve SAA as a composite measure of the following:

- Rates of TRSAE (treatment related serious adverse events) compared to standard regimen (protocol 12-H-0150). TRSAE are defined in section 9.5.
- Rates of mis- and altered diagnoses compared to standard regimen. **Misdiagnosis** is defined as diagnosis of other hematological or non-hematological condition to explain peripheral pancytopenia such as myeloid neoplasm.
- Number and proportion of patients who are unable to comply with the outpatient early drug regimen and withdraw from study or who do not present to the Clinical Center for evaluation within 8 weeks (or within allowed grace period in special circumstances defined in section 9.6)

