9.3 SAMPLE SIZES AND STATISTICAL DESIGN

Cohort 1: Since safety and feasibility is defined in Section 9.1 to be the primary endpoint of this study, the treatment is defined to be “feasible” to a patient if he/she meets the safety and feasibility criteria specified in Section 9.1 at the end of study treatment period. Study treatment period is defined as the duration from the initiation of oral treatment to the start of standard of care treatment here at NIH. “Feasibility” is defined as tolerating treatment without the composite of TRSAE/misdiagnoses/noncompliance (defined in section 9.1). Our past experience with the standard 3 drug regimen (12-H-0150) suggests that the probability of feasibility for this patient population is approximately 90%. We hypothesize that the actual feasibility probability using this novel treatment paradigm may decrease to 75%, therefore a probability of 75% or less would warrant terminating this novel treatment approach. The hypotheses are equivalent to $H_0: p \leq 75\%$, in which feasibility is unacceptable, and $H_1: p \geq 90\%$, in which feasibility is acceptable. Our sample size is determined by testing this hypothesis at a significance level of 0.05 and 0.80 power. We intend to test this treatment approach using a small number of patients and terminate the study if early evidence suggests that the feasibility probability diminishes below the benchmark of 75%. We determine the sample size using the Two-Stage Minimax Design of Simon (1989), since it requires a smaller total number of subjects ($n = 39$) compared to the Two-Stage Optimal Design ($n = 48$). At the first stage, 22 subjects will be accrued, and the null hypothesis will be accepted if 17 or fewer subjects are determined to be feasible to the treatment within defined treatment period. Therefore, if 18 or more subjects are feasible to the treatment at the first stage, 17 additional subjects will be accrued. The null hypothesis of $p \leq 75\%$ will be accepted if the total number of patients feasible to the treatment are 33 or fewer.

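### The Section 9.5 stopping rule stops counting TRSAEs at Clinical Center evaluation, while the Section 9.3 study treatment period runs to the start of standard treatment; the two windows should be one.

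*Combined protocol and SAP*

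**What the plan says.** **Stopping rule (Section 9.5).** TRSAEs are monitored over a period of up to 8 weeks, or the grace period, "from initiation of oral therapy until evaluation at the clinical center". The first item in the event list uses different wording: "Death considered to be probably or definitely related to the oral treatment during the study treatment period". The grade IV item and the item on death related to misdiagnosis carry no window of their own.

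**Primary endpoint (Sections 9.1 and 9.3).** A patient is feasible if he or she "meets the safety and feasibility criteria specified in Section 9.1 at the end of study treatment period", and that period is "the duration from the initiation of oral treatment to the start of standard of care treatment here at NIH". Section 9.1 refers back for its event definition: "TRSAE are defined in section 9.5".

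**Timing (Sections 3 and 5, Schedule of Events).** Without a grace period, evaluation falls within 8 weeks of starting oral drugs, but Section 5 adds that "the administration of the standard treatment may not occur within the 8 weeks" time frame. For early arrivals, Section 3 says: "Patients will be evaluated and enrolled at the NIH if able to arrive for initial visit within 72 hours of referral". Section 5 has these patients start oral drugs on evaluation there, and the Schedule of Events places their baseline and first visit at the same time. Section 3 describes oral treatment at the NIH during work-up.

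**The concern.** The trial exists to test the oral-only phase, so its toxicity rule should cover that phase. As written, the rule closes at evaluation, while oral-only treatment can continue until standard treatment starts. There are three consequences:

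- A remote starter's TRSAE between evaluation and standard treatment counts toward feasibility under 9.3 but not toward the 9.5 boundary.
- An on-site starter begins oral drugs at about the moment the 9.5 window closes. That subject can add little or nothing to the event count, yet is one of the treated subjects on whom the boundary is indexed.
- Section 9.5 uses both windows, and 9.1 takes its event definition from 9.5. Two people applying the text in good faith could reach different counts.

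At stake is which events can trigger a stop, and whether the reported operating characteristics can be read as describing the oral phase.

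**Working it through.** **Step 1. Set the two windows side by side.**

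| | Start | End | Used for |
|---|---|---|---|
| Section 9.3 | first oral treatment | start of standard treatment | primary composite |
| Section 9.5, lead-in | first oral treatment | evaluation at the Clinical Center | stopping rule |
| Section 9.5, first death item | uses the 9.3 term | uses the 9.3 term | stopping rule |

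Section 5 allows the two end dates to differ. Section 2.3.7 reports time on oral therapy of 0 to 86 days (median 14). The maximum exceeds 56 days, but the time between evaluation and standard treatment is not reported separately.

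**Step 2. Reproduce the plan's boundary.** Inputs from Section 9.5: prior Beta(1.10, 4.40), benchmark 20%, posterior threshold 90%, monitoring from 3 affected subjects. The boundary at n subjects is the smallest x ≥ 3 with

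P(p > 0.20 | Beta(1.10 + x, 4.40 + n − x)) ≥ 0.90.

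At n = 5, x = 3 this probability is 0.909; at n = 39, x = 12 it is 0.926. The printed boundary is reproduced at every n from 3 to 39.

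**Step 3. Reproduce the operating characteristics.** An exact binomial recursion checks the boundary after each of 39 subjects, in place of the plan's 100,000 simulations.

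| True rate of monitored TRSAE | 5% | 10% | 15% | 20% | 25% | 40% |
|---|---|---|---|---|---|---|
| Plan: stopped | 0.15% | 1.62% | 7.26% | 21.74% | 44.48% | 95.30% |
| Exact: stopped | 0.15% | 1.57% | 7.33% | 21.65% | 44.40% | 95.30% |

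The differences are within simulation error.

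**Step 4. Show what uncounted events would do.** Let p be the true oral-phase rate and m the share of those events that falls outside the 9.5 window. The rule then sees p × (1 − m). The documents do not give m, so it is an assumption shown over a range. The 30% rate is also an assumption; 25% and 40% are in the plan's own table.

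| p | m = 0 | m = 10% | m = 20% | m = 30% | m = 50% |
|---|---|---|---|---|---|
| 25% | 44% | 32% | 22% | 13% | 3.6% |
| 30% | 68% | 54% | 39% | 26% | 7.3% |
| 40% | 95% | 89% | 77% | 59% | 22% |

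One entry can be checked against the plan's table alone. With p = 25% and m = 20%, the monitored rate is 0.25 × 0.80 = 20%, which the plan tabulates at 21.74%. If a share s of subjects starts on site with no counted exposure and equal event risk, m is at least s. The documents do not report s.

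**Step 5. Check Cohort 1.** Section 2.3.7 reports 0 composite events in 36 subjects. Even if the remaining three of 39 all had events, the count would be 3, against a boundary of 12 at n = 37 to 39.

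**The case against.** **The table is conditional on monitored events.** Section 9.5 labels its simulation parameter as the probability of a monitored TRSAE. A reader might infer that the operating characteristics are wrong, or that the rule is less sensitive than the plan claims. The documents do not support that: the figures are right for the events the rule counts. They simply do not carry over to the whole oral phase unless all of its events are counted.

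**Other safeguards remain.** A reader might infer that late oral-phase toxicity goes unseen. It does not. SAEs are collected from the first dose for as long as the subject is on study (Section 10.6.2), the DSMB reviews every 6 to 12 months (Section 10.1), and under 9.3 a TRSAE is a feasibility failure. At a 30% TRSAE rate with no other failures (feasibility 70%), the Simon first stage (17 or fewer of 22) stops 83.5% of studies and only 1.1% pass the final test. This stands, with two limits: the Simon design covers Cohort 1 only, and it has a single interim look.

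**An empty on-site window is one reading.** If evaluation means completed work-up rather than the first visit, on-site starters have some monitored exposure. Sections 5 and 9.1 tie evaluation to presenting within 8 weeks, which favors the first visit, but the term is not defined. Some on-site patients may have no oral-only phase, because Section 3 lets all three drugs start together if ANC is below 200 at the initial visit. It is therefore too strong to say that all on-site starters have zero monitored exposure. On either reading, time between evaluation and standard treatment is uncounted.

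**The intent may be the 9.3 window.** The death item in 9.5 suggests so. That supports aligning the text; it does not remove the conflict.

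**The extension.** The printed boundary ends at 39 subjects. Sharing the study design does not show that this boundary governs the 41 further subjects, so the probabilities above are not a statement about them.

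**Conclusion.** The conflict is real and is one of definition. Taken literally, the 9.5 lead-in leaves oral-only exposure after evaluation out of the stopping rule while keeping those subjects in its denominator, and 9.5 is inconsistent with itself.

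The size cannot be stated from the documents. It depends on the uncounted share, the true rate and the meaning of evaluation. The fall from 68% to 39% (30% true rate, 20% uncounted) illustrates one layer of monitoring; it does not estimate what happened or the trial's overall protection.

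Nothing suggests that a Cohort 1 decision was affected. One check remains: because 9.1 borrows its TRSAE definition from 9.5, the text does not settle which window produced the reported zero. The sponsor can confirm this from recorded events.

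**What to change.** Replace the 9.5 window with the 9.3 study treatment period: first oral dose to the start of standard treatment, wherever that treatment is given (Section 5 allows local administration, whereas the 9.3 wording refers to the NIH only). Use the same window in 9.1, 9.3 and 9.5 for every item in the TRSAE list. Have the sponsor state an analysis end date for complete responders who omit h-ATG, for whom 9.3 gives none. Confirm the TRSAE count to date under this window.

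The cost is a few lines of text and a review of events already collected. No treatment or visit changes. The boundary can stay, and its published operating characteristics would then apply to the whole oral phase. The downside is that the monitored count may be slightly higher.

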10.5 SERIOUS ADVERSE EVENTS (SAEs) CHARACTERIZATION

Serious adverse events will be attributed as definitely (clearly related to the research), probably (likely related to the research), possibly (may be related to the research), unlikely (doubtfully related to the research) and unrelated (clear not related to the research).

TRSAEs are those attributed as definitely or probably related to treatment. As detailed in section 9.5 stopping rules, TRSAE that will be monitored and considered for early stopping the study according to statistically determined criteria include Death and any grade IV toxicity considered to be probably or definitely related to study medication.

Note that hospitalizations for the following reasons will not be captured as serious adverse events, as these hospitalizations are not a result of an adverse event:

Abbreviated Title: Early Initiation of Oral Therapy for Naïve Severe Aplastic Anemia (SAA)

Version Date: 11/05/2025

- Routine treatment or monitoring, not associated with any deterioration in condition
- Hospitalizations for administrative issues (e.g., to receive a transfusion after hours) or movement to the ICU for routine monitoring per administrative requirements or nosocomial isolation
- Elective or pre-planned treatment for a pre-existing condition that is unrelated to the indication under study and has not worsened since signing the informed consent
- Social reasons and respite care in the absence of any deterioration in the patient's general condition

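### Two components of the primary composite, treatment-related SAE attribution and non-compliance, are each defined in two conflicting ways, and the reported 0 events in 36 does not say which wording was applied

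*Combined protocol and SAP*

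**What the plan says.** **TRSAE attribution.** The primary endpoint section delegates the definition: "TRSAE are defined in section 9.5". Section 9.5 then lists three monitored events as bullets.

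- The first concerns fatal events and refers to both oral drugs together: "Death considered to be probably or definitely related to the oral treatment during the study treatment period".
- The second concerns toxicity and again singles out neither drug: "Any grade IV toxicities considered to be probably or definitely related to the treatment".
- The third carries no drug attribution at all: "Death related to misdiagnosis and delay in appropriate treatment".

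The next paragraph adds: "TRSAEs are those attributed as definitely or probably related to eltrombopag". Section 10.5, which refers back to 9.5, words it differently: "TRSAEs are those attributed as definitely or probably related to treatment". It describes the monitored events as "Death and any grade IV toxicity considered to be probably or definitely related to study medication". The 20% benchmark in 9.5 is introduced with "From our experience using this agent in other clinical settings", in the singular.

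**Non-compliance.** Section 9.1 counts patients who cannot comply with the early oral regimen and also withdraw, or who do not present at the Clinical Center within 8 weeks or the grace period. Section 9.3 names 9.1 as the definition of the composite. Section 7, under a heading specific to feasibility, counts the missed visit, failure to comply with the oral drugs, or failure to comply with clinical or laboratory assessment. It sets no withdrawal condition.

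**Reported result.** Section 2.3.7 says the primary endpoint was met with 0 composite events after 36 subjects. It names the three components but not the definitions applied.

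**The concern.** The regimen under test has two drugs. A grade IV toxicity attributed only to cyclosporine is an event under the 9.5 bullets and 10.5, but not under the sentence that follows the bullets. That sentence feeds both the primary composite (through 9.1) and the safety stopping count. Likewise, a patient who stops taking the oral drugs but stays on study and reaches the Clinical Center in time is a failure under Section 7 and a success under 9.1.

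At stake is what 0 of 36 means. The readings are nested: every event under the narrow wording (eltrombopag-only attribution, withdrawal required) is also an event under the wide one. If the wide wording gave 0, the narrow count is 0 too and the matter is closed. If the narrow wording gave 0, cyclosporine-only events and non-compliance without withdrawal were never eligible to be counted. The extension cohort keeps the same study design, so the unreconciled text carries forward.

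**Working it through.** **1. The design itself (9.3).** Inputs: unacceptable rate 0.75, acceptable rate 0.90, significance level 0.05, power 0.80; stage 1 accepts the null at 17 or fewer feasible of 22, the final stage at 33 or fewer of 39.

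P(declare feasible | p) = sum over x = 18 to 22 of Bin(x; 22, p) × P(Y ≥ 34 − x), with Y ~ Bin(17, p).

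- p = 0.75: 0.0498
- p = 0.90: 0.802

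A full search returns this as the minimax design (n = 39), with n = 48 for the optimal design, as stated. The 9.5 boundary also matches its posterior rule (Beta(1.10, 4.40) prior, 20% benchmark, 90% posterior probability) at every n from 3 to 39. The arithmetic is sound; the problem lies in what counts as an event.

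**2. The wordings side by side.**

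| Case | 9.1, with the eltrombopag sentence of 9.5 | 9.5 bullets, 10.5, Section 7 |
|---|---|---|
| Grade IV toxicity, cyclosporine only | not an event | event |
| Oral-drug non-compliance, no withdrawal | not an event | event |
| Missed clinical or laboratory assessment, no withdrawal | not an event | event (no threshold given) |
| No visit by 8 weeks or grace period | event | event |
| Death from misdiagnosis | event, through the misdiagnosis component | event |

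The last row shows that the clash between the eltrombopag sentence and the third bullet affects the stopping count only, not the composite.

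**3. Effect on the decision.** Let m be the number of the 36 who become failures under the wider wording. The final rule needs at least 34 feasible of 39, and the outcomes of patients 37 to 39 are not given.

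- m ≤ 2: 36 − m ≥ 34, so the rule is already met.
- m = 3, 4, 5: 33, 32 or 31 feasible so far, so at least 1, 2 or 3 of the last three must be feasible.
- m ≥ 6: at most 30 + 3 = 33, so the null is accepted.
- Stage 1: 5 or more among the first 22 leaves 22 − 5 = 17 or fewer, so the trial would have ended there.

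**4. Effect on the estimate.** Exact (Clopper-Pearson) two-sided 95% lower limits for feasibility:

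| Feasible | Lower limit |
|---|---|
| 36/36 | 90.3% |
| 39/39 | 91.0% |
| 38/39 | 86.5% |
| 37/39 | 82.7% |
| 36/39 | 79.1% |

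With no failures the limit is 0.025^(1/n), for example 0.025^(1/36) = 0.903. One failure in 39 lowers it by 91.0 − 86.5 = 4.5 points. The number reclassified is not in the documents, so the 0 to 3 failures shown are an illustration.

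**The case against.** Context settles much of this. The threshold, benchmark, posterior rule and simulation in 9.5 all refer back to the listed events, two of which are tied to the treatment as a whole, and 10.5 agrees. One sentence is outvoted, although the singular agent behind the 20% benchmark leans the other way. For non-compliance, 9.3 names 9.1 as the source. Section 9.6 adds that subjects who fail to comply may be taken off study, which partly bridges Section 7 and the withdrawal condition; because removal is optional, the bridge is incomplete. These points show which reading was probably intended. They do not show which was applied.

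A reader might infer from 5.12, which lists malignant hypertension with encephalopathy and acute renal failure among common reasons for treatment-related admission, that cyclosporine-only events were probably missed. The documents do not support that. Section 5.12 is not limited to the low-dose phase or to grade IV events. Section 12.3.2 says nephrotoxicity is rare with low-dose cyclosporine, and 2.3.7 gives a median of 14 days on oral therapy.

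A reader might also infer that the safety stopping rule was compromised. Showing that would need a cyclosporine-only share of events, which the documents do not give. The boundary at 36 patients is 11 events, and the table ends at 39 patients, whom 9.3 describes as already accrued.

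**Conclusion.** The point stands as a conflict of definitions. Followed literally, the eltrombopag sentence in 9.5 would miscount a primary component and a safety count for a two-drug regimen, and 9.1 and Section 7 disagree on whether non-compliance needs withdrawal. The stronger reading, that 0/36 is wrong or that feasibility was not shown, is not supported: no document shows a patient who would be reclassified, and low-dose cyclosporine toxicity is expected to be infrequent.

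The feasibility conclusion is safe for up to 2 reclassified patients and certain to reverse only at 6 or more, or at 5 or more within the first 22. The likelier consequence is a somewhat lower reported estimate. This rests on 0 events in 36 as reported, with the last three patients unknown. Severity is minor to should-fix: the text conflict is certain, its consequence is not.

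**What to change.** 1. In 9.5, change the attribution in the quoted sentence from eltrombopag to the oral treatment (cyclosporine and/or eltrombopag), in line with the bullets and 10.5. Keep the misdiagnosis-death bullet as a separate item. Confirm that the 20% benchmark is meant for the two-drug regimen.
2. Align Section 7 with 9.1, the definition that 9.3 cites. Add no new laboratory-compliance threshold: 10.3 already expects about 50% of monitoring tests in the first 6 months to fall outside their window, so a literal laboratory criterion could turn many patients into failures after results are known.
3. State which wording of each component produced 0/36. If any was the narrow one, leave that result as applied. Beside it, as a sensitivity analysis, give the feasible count under the wider reading (any-oral-drug attribution; documented oral-drug non-compliance without withdrawal), with its exact 95% confidence interval, against both thresholds: 18 of 22 and 34 of 39. List each case so that no cut-off is chosen afterwards.

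**Cost.** Wording changes in 9.5 and Section 7, plus one statement. Only if a narrow wording was used: a review of up to 39 patients' SAE reports, weekly call notes and medical records. Grade IV events not reported as SAEs may need their attribution checked, since 10.4 attributes adverse events to study medication without separating the drugs. The feasibility estimate may become slightly less favourable.
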